7 STATISTICAL METHODS

7.1 General Principles

All data processing, summarization and analyses will be performed using the SAS Version 9.3 (or later) of the SAS® statistical software package.

All data collected will be sorted and presented in listings by treatment group, site, patient identification, assessment, relative day (see Section 6.1 for definition) and visit (where applicable), unless otherwise specified.

Data will be presented in summary tables by treatment group (revusiran, placebo), assessment and visit (where applicable).

Descriptive summary statistics for continuous variables will include the number of patients/observations (N), mean, standard deviation (SD), median and range (minimum, maximum).

Descriptive summary statistics for categorical variables will include frequency counts and percentages for each category [n (%)]. A category of missing will be included if the number missing is greater than zero. Unless stated otherwise in the table shells, the denominator for percentage calculations will be the number of patients in the analysis population.

All statistical tests will be 2-sided and performed at the 5% significance level, unless otherwise specified. Confidence intervals of 95% will be provided where appropriate.

7.2 Subject Disposition and Data Sets Analyzed

Patient disposition will be listed and summarized by treatment group and will include the number and percentage of patients:

- Enrolled (signed informed consent and met eligibility)
- Randomized
- Treated
- mITT population
- Safety population

• Per-Protocol population

Summaries of the number and percentage of patients who completed the study, who completed study treatment, who discontinued study treatment and completed the remainder of required study visits through Month 18, who discontinued study treatment but did not complete the remainder of required study visits, and the primary reasons for study and treatment discontinuation will be presented for all randomized patients.

Descriptive statistics will also be presented for time from first dose of study drug to discontinuation of study treatment (months) and there will be a summary of the number (percentage) of patients who discontinued study treatment at 3 month intervals.

In addition, descriptive statistics of the difference in days from time of randomization to date of first dose of study drug will be provided in a separate table.

A summary of patients randomized by country and site will be provided by treatment group for all patients randomized.

7.3 Protocol Deviations

All protocol deviations leading to exclusion from the PP population (see Section 5.3.1) will be listed and summarized by treatment group for the mITT population. In addition, all protocol deviations (major and minor) will be summarized in a separate listing.

The deviations will be identified before data are unblinded.

7.4 Demographics and Other Baseline Characteristics

Demographic and baseline characteristics will be listed and summarized by treatment group for mITT and PP analysis populations. Standard descriptive statistics will be presented for the following:

Demographics:

- Age at randomization (years) and Age categories
- Gender
- Race
- Ethnicity
- Regions (North America, Europe, Rest of World)
- Body weight (kg) and categories
- Height (cm)
- BMI (kg/m²)
- Modified BMI and categories
- Genotype

Stratification factors (note: summarized separately based upon responses in IVRS and eCRF):

- 6-MWD (meters) and 6-MWD categories (<325 vs. >325 meters)
- TTR mutation categories (V122I, other FAC mutations)
- NYHA categories (I, II vs. III)

Other key baseline disease characteristics:

- Karnofsky Performance Status
- Time from ATTR diagnosis to informed consent (years)
- eGFR
- PND Score

Patients will be categorized in a region based upon the location of the clinical site.

An additional per patient listing will be provided of other screening test results such as Vitamin A, serum protein electrophoresis (SPEP) with immunofixation (IFE), urine SPEP with IFE, and serum free light chain (FLC) and Hepatitis B surface antigens (HBsAg), Hepatitis B surface antibodies (HBsAb) and Antihepatitis C virus antibodies (HCV Ab).

7.4.1 Medical History

Medical history will be coded using the Medical Dictionary for Regulatory Activities (MedDRA) Version 17.1 or later. All medical history will be provided in a data listing, and the number and percentage of patients with any medical history will be summarized for the mITT analysis population by system organ class (SOC) and preferred term (PT) for each treatment group.

Additional listings will also be provided for any other prior surgeries noted at screening.

7.4.2 Previous and Concomitant Medications

Medications received prior to or concomitantly with study drug will be coded by using the WHO Drug Dictionary Version March 2014 or later.

Prior medications and concomitant medications are defined as follows:

Prior medications are medications that stopped prior to the first dose of study drug.

Concomitant medications are those with a start date on or after the first dose date of study drug, or those with a start date before the first dose of study drug and are continued after the date of first dose of study drug.

Prior medications, prohibited medications, concomitant medications taken during treatment phase, and medications started after the last dose of study drug will be summarized in a table by ATC classification and preferred term by treatment group.

Prior medications, prohibited medications, and concomitant medications will be provided in data listings.

In addition, a separate listing of diuretic medications prior and concomitant will be generated by treatment group. Any medication classified with ATC classification "C03C" based on the World Health Organization Drug Dictionary are considered diuretic medication.

7.5 Extent of Exposure

Study drug exposure will include descriptive statistics of the duration of treatment (months) and total number of doses of study drug by treatment group. Additional summaries of the cumulative number of patients (percentage) that completed study treatment at visit intervals (e.g. <3 months, 3-6 months) and the number of patients (percentage) that completed study treatment at the latest visit interval will also be displayed by treatment group. The cumulative number of patients (percentage) that received doses in each

Version: 1.0

Alnylam Protocol No. ALN-TTRSC-004

interval (e.g. loading dose, <12 doses) and the number of patients (percentage) that completed the total number of doses at the interval will also displayed by treatment group.

7.6 Efficacy

All efficacy analyses will be performed on the mITT population. In addition, the analysis of the coprimary efficacy endpoints will be also be evaluated using the PP population.

Where appropriate, analyses will be stratified based upon a subset of stratification parameters used for randomization: TTR mutation (V122I versus other FAC mutations), and 6-MWD (≤325 meters versus >325 meters). The values of these stratified parameters will be based upon the data entered in the eCRF.

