1.4. Study Design Rationale

This is a Phase 3 randomized, double-blind, placebo-controlled, multicenter, multinational study to evaluate the efficacy and safety of ALN-TTRSC in FAC patients. The patients proposed for this study are reflective of the FAC population encountered by clinicians in various different countries worldwide, including patients with a range of disease severity and spectrum of TTR mutations.

The target population for this study is FAC patients with clinical evidence of mild-to-moderate heart failure. The study is being restricted to FAC in order to minimize the phenotypic heterogeneity and focus on a genetically-defined population where the disease pathogenesis is more clearly defined and where there is the greatest unmet need. Patients with FAC appear to have more rapid disease progression compared to patients with SSA, thereby providing a greater opportunity to demonstrate a disease-modifying effect with ALN-TTRSC treatment. Heart failure severity will be limited to New York Heart Association (NYHA) class I, II and III, and patients must have a Karnofsky performance status of ≥ 50%. Since a 6-minute walk distance (6-MWD) of <150 meters is associated with early poor outcomes, ^{16,17} and since disease in such patients may be too advanced to be impacted by ALN-TTRSC, eligible patients must minimally have a 6-MWD of ≥150 meters. Analysis of the UK natural history dataset (National Amyloidosis Center, unpublished results) that includes information on both 6-MWD and NYHA class suggests that a 6-MWD cut-off of 150 meters will enrich for NYHA class I-II and early class III patients.

The inclusion of placebo as a control allows for unbiased analysis of the treatment effect of ALN-TTRSC on TTR-mediated FAC. Saline will be used as placebo. FAC is currently managed by treatment of symptoms, mostly with the use of diuretics and antiarrhythmic drugs, which will be permitted during the study.

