Given the orphan nature of the disease and the significant, progressive morbidities associated with FAC, randomization to ALN-TTRSC or placebo will be performed in a 2:1 ratio (ALN-TTRSC:placebo) to increase the probability that patients will receive active drug. Since NYHA class and 6-MWD are predictive of outcomes in heart failure, ^{18,19} treatment groups will be balanced at entry for NYHA classification (I and II vs III), and Screening 6-MWD (≤325 meters vs >325 meters). Patients will also be stratified for V122I versus all other mutations, in order to balance for phenotypic heterogeneity among the different FAC mutations with the prognosis being worse for V122I (the most common FAC mutation worldwide) compared to T60A, ^{7,9} and outcomes less well described for other FAC mutations is considered prudent.

The co-primary endpoint for this study is the change from baseline in meters walked during the 6-minute walk test (6-MWT) at 18 months and percent reduction from baseline in serum TTR levels over 18 months compared between treatment groups. Serum TTR levels are expected to reach nadir within approximately 3 weeks following the onset of dosing. The 18-month endpoint was selected based on the rapid rate of 6-MWD decline with V122I FAC patients, derived from a natural history dataset from the UK (National Amyloidosis Center, unpublished results) and the prospective TRACS study. From these data it is estimated that FAC patients decline in 6-MWD by 74 to 118 meters in 18 months, thereby providing adequate disease progression for the detection of a treatment effect in ALN-TTRSC treated patients. The clinical relevance of TTR lowering is supported by improved survival of patients with FAP after liver transplantation of circulating amyloidogenic protein. It is anticipated that a marked, sustained reduction in serum TTR levels over 18 months by ALN-TTRSC will result in stabilization or improvement in cardiac amyloid deposition, with a corresponding beneficial effect on cardiac function and clinical outcomes, including the 6-MWD.

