3. INVESTIGATIONAL PLAN

3.1. Overall Study Design

This is a multicenter, multinational, randomized, double-blind, placebo-controlled Phase 3 study designed to demonstrate the clinical efficacy and safety of ALN-TTRSC in patients with TTR mediated FAC.

Approximately 200 consented eligible patients will be randomized to receive either ALN-TTRSC or placebo at a 2:1 ratio (ALN-TTRSC to placebo) in a blinded manner as a subcutaneous administration. Treatment groups will be balanced at randomization for NYHA classification (I and II versus III), TTR mutation (V122I versus other FAC mutations), and 6-MWD (≤325 meters versus >325 meters). Patients will receive ALN-TTRSC or placebo daily for 5 days during the first week, a single dose on Day 7, and then once weekly for 18 months.

Patients will undergo efficacy and safety assessments at Screening/Baseline, each month for first 3 months, and then at 3-6 month intervals.

The duration of patient participation in this study is approximately 20 months (inclusive of up to a 45 day Screening/Baseline window and up to 35 days of follow-up after the last dose).

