9.2.3. Efficacy Analyses

9.2.3.1. Primary Efficacy Endpoint

There are two co-primary endpoints. The first co-primary endpoint is change from baseline (in meters) for a 6-MWD conducted 18 months after randomization. The primary efficacy analysis for the comparison of 6-MWD between treatment groups will be conducted using Wilcoxon Mann Whitney-based test statistics that will take into account informative missingness due to death and the loss of the ability to perform the test. Briefly, in this stratified non-parametric rank sum analysis, all pairs of patients within a stratum are compared. A pair of patients is compared first on time to death (if death occurs before 18 months); second on time until the inability to perform the test (if it cannot be determined as to which patient in a pair lived longer); and third on the change from baseline in 6-MWD at the time of the last assessment shared by both patients (if it cannot be determined as to which patient in a pair lived longer and which retained the ability to perform the 6-MWD longer). The analysis will be stratified based on the stratification parameters that are used for randomization.

The second co-primary endpoint is percent reduction from baseline in serum TTR using enzyme-linked immunosorbent assay. The area under the effect curve (eAUC) for percent reduction from baseline in serum TTR over time, where the y-axis is percent reduction and the x-axis is time since randomization, will be compared across groups using Analysis of Covariance (ANCOVA), in which the stratification variables and baseline serum TTR level will be included in the model as covariates. The eAUC will be computed using the trapezoidal method, where assessments missing due to death or discontinuation will be imputed using the baseline level, i.e., the percent reduction will be assumed to be 0%.

The study will have demonstrated efficacy if the p-value for each of the co-primary endpoints is \leq 0.05 (2-sided).

Sensitivity analyses for each co-primary endpoints, including different methods for handling of the missing data, will assess the robustness of the primary analysis for the mITT population.

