9.2.3.2. Secondary Efficacy Endpoints

The secondary composite of CV mortality and CV hospitalization, as well as change in NYHA class and change in KCCQ, will also be compared across treatment groups using stratified Finkelstein and Schoenfeld Joint Rank Tests. CV mortality and all-cause mortality will be compared across treatment groups using stratified log-rank tests. CV hospitalizations will be compared using the stratified Anderson-Gill model for recurrent events. Analyses will be stratified using the stratification parameters that are used for randomization.

Type I error control for secondary endpoints will be achieved by a hierarchical ordering procedure. Endpoints will be compared across treatment groups in the following pre-specified order:

- Composite CV mortality and CV hospitalization
- New York Heart Association (NYHA) class (Appendix 1)
- Kansas City Cardiomyopathy Questionnaire (KCCQ)

- Cardiovascular (CV) mortality
- CV hospitalization
- All-cause mortality

If and only if a comparison is significant at p<0.05, the next endpoint in the hierarchy may be formally tested.

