7.6.1.3 Percent reduction in serum TTR from Baseline over 18 months

The primary analysis for the co-primary endpoint of percent change in TTR from baseline over 18 months will be analyzed using an Analysis of Covariance (ANCOVA) model.

The dependent variable used in the ANCOVA model w	rill be area under the effect curve (eAUC) to			
quantify the percent reduction in TTR from baseline over 18 months. The covariates used in the model				
will be treatment group, TTR mutation	and 6-MWD at Screening			
and baseline TTR serum levels. The	difference in the adjusted mean eAUC between			
treatment groups will also be presented with associated 95% confidence interval. The dependent variable				
will be log transformed.	-			

Calculation of eAUC will be based on trapezoidal method, where the y-axis is percent reduction in serum TTR and the x-axis is time since first dose of study drug. Assessments missing due to death or discontinuation will be imputed using the baseline value, and thus the percent change will be 0%. The span of time will start at time 0 (baseline) and end at month 18. Only scheduled visits will be included in the calculation of eAUC.

7.6.1.4 Sensitivity Analyses for Percent Reduction in Serum TTR from Baseline over 18 months

Sensitivity #1: Address impact of baseline factors

The eAUC will be analyzed using an unadjusted ANOVA model. The covariates of the model will be treatment group and the dependent variable will be eAUC.

Sensitivity #2: Address robustness using a different distributional assumptions

A mixed-effects model repeated	l measures (MMRM) ana	alysis based on the re	stricted maximum likelihood
(REML) method for estimation w	vill be performed for rela	tive fold change in s	serum TTR. The dependent
variable will be relative fold cha	ange defined as (TTR va	lue at follow-up visi	t/baseline TTR value). The
covariates used in the model wil	ll be treatment group, vis	sit, treatment group b	by visit interaction, TTR
mutation	and 6-MWD at Screeni	ng	and baseline
TTR serum levels. The difference	ce in the adjusted mean i	relative fold change	n serum TTR between
treatment groups and associated	95% will also be presen	ited. The dependent	variable will be log
transformed.			

Sensitivity #3: Address influence of missing data

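### The SAP drops NYHA class from the strata that the protocol prescribes for the primary and secondary tests, and no reason is visible

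*SAP*

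**What the plan says.** Protocol 3.1 sets three randomisation factors: "Treatment groups will be balanced at randomization for NYHA classification (I and II versus III), TTR mutation (V122I versus other FAC mutations), and 6-MWD" (cut at 325 m). SAP 2.2 lists the same three.

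For the analysis, the documents part:

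- **6-MWD joint rank test.** Protocol 9.2.3.1: "The analysis will be stratified based on the stratification parameters that are used for randomization".
- **Serum TTR ANCOVA.** Protocol 9.2.3.1 describes a model "in which the stratification variables and baseline serum TTR level will be included in the model as covariates".
- **Secondary tests.** Protocol 9.2.3.2: "Analyses will be stratified using the stratification parameters that are used for randomization". The synopsis agrees on all three.
- **SAP 7.6**, as a general rule for efficacy, where appropriate: "analyses will be stratified based upon a subset of stratification parameters used for randomization: TTR mutation" (V122I or other) and 6-MWD (≤325 m or >325 m), using eCRF values. NYHA is not in the list.
- **SAP 7.6.1.3.** The visible ANCOVA terms "will be treatment group, TTR mutation", screening 6-MWD and baseline TTR match the two-factor rule, although that line has gaps.

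In the SAP, NYHA remains a baseline summary (7.4), a subgroup (7.6.1.5) and the subject of its own secondary endpoint (7.6.2.2). It is not a stratum or a visible covariate.

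**The concern.** Protocol 1.4 explains the choice of factors: "Since NYHA class and 6-MWD are predictive of outcomes in heart failure". The SAP keeps 6-MWD and drops NYHA, although the protocol gives one reason for both.

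Efficacy requires p ≤ 0.05 on each co-primary endpoint, and the secondary hierarchy stops at the first failure. If one p-value has two written definitions, the choice between them could be made, or be suspected of having been made, after unblinding. No visible text says which document prevails. Protocol 9.2 says only that a full SAP will be finalised before database lock. The SAP (21 October 2015) was written from protocol version 1.0 of October 2014. The supplied protocol cites data from January 2016 and still calls for the randomisation factors.

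**Working it through.** **1. The planned power.** Inputs from Protocol 9.1: 120 and 60 patients, 0.55 SD (39 m / 70 m = 0.557), deaths 13% and 20% by month 18, two-sided 0.05. An unstratified joint rank test (exponential deaths, normal change in survivors, no loss-of-ability tier, 20,000 runs) gives power 0.890 at 39/70 SD and 0.880 at 0.55 SD, against the stated 90%. The plan's figure is thus roughly reproduced without strata. Enrolment: 180 / 0.90 = 200.

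**2. Strata.** Protocol: 2 × 2 × 2 = 8. SAP: 2 × 2 = 4.

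**3. Assumptions.** The documents give no NYHA prevalence or effect. Assumed: 35% class III, 60% V122I, 45% with 6-MWD ≤325 m. Effect of class III: none; moderate (0.4 SD, death HR 2); strong (0.7 SD, HR 2.5). NYHA is taken as independent of 6-MWD or correlated 0.5. Some correlation is likely, since Protocol 1.4 says natural history data "suggests that a 6-MWD cut-off of 150 meters will enrich for NYHA class I-II and early class III patients".

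**4. Statistic.** In stratum s, with n_s patients of whom m_s are treated, S_i is the number of patients that patient i beats minus the number that beat i.

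- `T_s = sum of S_i over treated patients`
- `V_s = m_s(n_s − m_s) / [n_s(n_s − 1)] × sum of S_i²`
- `Z = Σ w_s T_s / √(Σ w_s² V_s)`, with w_s = 1 (unweighted) or 1/(n_s + 1) (weighted)

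**5. 6-MWD results under the planned effect.** N = 180, 0.55 SD, blocks of 6 within the eight randomisation strata, 20,000 runs per cell (Monte Carlo SE about 0.25 point). Changes are in power points from unrounded values. Disagreement is the share of trials where only one of the two tests reaches p ≤ 0.05.

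| NYHA effect, relation to 6-MWD | Unweighted power, 4 → 8 strata | Change | Disagree | Weighted power, 4 → 8 strata | Change | Disagree |
|---|---|---|---|---|---|---|
| None, independent | .861 → .828 | −3.3 | 6.5% | .877 → .869 | −0.8 | 2.8% |
| None, correlated | .858 → .802 | −5.6 | 8.5% | .875 → .869 | −0.7 | 2.5% |
| Moderate, independent | .860 → .844 | −1.6 | 5.7% | .877 → .881 | +0.4 | 2.9% |
| Moderate, correlated | .867 → .821 | −4.6 | 7.6% | .883 → .881 | −0.2 | 2.8% |
| Strong, independent | .862 → .869 | +0.7 | 5.2% | .878 → .900 | +2.2 | 3.9% |
| Strong, correlated | .869 → .845 | −2.4 | 6.1% | .886 → .900 | +1.5 | 3.2% |

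**6. Under the null.** Type I error is 3.8–4.9% with four strata and 4.7–5.1% with eight. The four-stratum test is conservative when NYHA is strongly prognostic. Disagreement is 2.6–3.2% unweighted and 1.4–2.1% weighted.

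**7. Sensitivity to prevalence.** With class III at 25–50%, 6-MWD ≤325 m at 30–50% and correlation 0.5 (8,000 runs), the weighted change is −0.9 to −0.4 points with no NYHA effect and +1.1 to +2.0 with a strong one. Unweighted, it is −6.4 to −3.9 and −3.2 to −1.3.

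**8. Sparse strata.** The smallest expected cell, if independent, is 180 × 0.35 × 0.40 × 0.45 = 11.3 patients. The smallest realised stratum averages 10.1 patients (3.4 placebo) if independent and 4.8 (1.6 placebo) if correlated. Expected deaths are 120 × 0.13 + 60 × 0.20 = 27.6. In the correlated case three to four of the eight strata have two or fewer deaths. Log-rank power for death is nonetheless similar: 24–25% with four strata and 24–26% with eight, with disagreement in 1.7–3.1% of trials.

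**The case against.** The word subset suggests that the omission was deliberate, and the SAP's list is explicit, so the SAP taken alone has one definition. A reason may sit in text missing from the supplied copy: the comparison steps in SAP 7.6.1.1, parts of the covariate lines, or Appendix II (the joint rank procedure). Restoring NYHA lowers power in 8 of the 12 comparisons above (5 of 6 unweighted, 3 of 6 weighted), and neither visible document specifies weights. The simulation omits the loss-of-ability tier and gives mutation and 6-MWD no prognostic effect of their own, which could flatter the gain from adding NYHA. Two valid tests will always disagree sometimes near p = 0.05, and for false claims the lower null rates matter more. A single SAP sentence recording the departure would be cheaper than a protocol amendment.

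Much of this stands. Two factors may be a sound choice, the power figures are illustrative, and only the absence of a visible reason can be claimed. It does not remove the discrepancy: the list in SAP 7.6 is intact, and the protocol still prescribes a different set. The power loss belongs mainly to unweighted strata, which weighting avoids. A sentence in the SAP would help, but the protocol would still state another primary analysis.

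**Conclusion.** The concern holds. The documents agree on endpoints and families of test but differ by one binary factor, in both co-primary analyses and, through the general rule in SAP 7.6, in the secondary tests (SAP 7.6.2 names no factors itself). That reading is firm.

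The consequence is moderate. Neither version inflates type I error, and the TTR comparison will hardly move. For 6-MWD, the two definitions would give different verdicts in a few percent of trials, fewer with weights than without. These rates rest on assumed prevalence, prognostic effect and correlation for NYHA. The matter should be settled before any unblinded look, but it does not make the planned test invalid.

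**What to change.** Give each test one definition before any unblinded look. The SAP update that section 7.8 foresees for futility criteria is a natural point.

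1. **Preferred: follow the protocol.** Amend SAP 7.6 so that NYHA (I/II or III) is a stratum in the joint rank tests and other stratified secondary tests, and a covariate in the TTR ANCOVA. Combine the joint rank strata with size-based weights such as 1/(n_s + 1), unless Appendix II already sets weights. Report the two-factor version as a sensitivity analysis. Adding NYHA to the MMRM sensitivity models is optional, since the protocol specifies none.
2. **Alternative: keep two factors for some or all tests**, for example the log-rank and Andersen-Gill analyses, with about 28 deaths expected. Amend the protocol to say so, state the reason (for example sparse strata), and make the three-factor version the sensitivity analysis.

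Option 1 is a text change using data already collected: SAP 7.4 summarises NYHA from both IVRS and eCRF. Its downside is sparse strata: at most about 1 power point with weights if NYHA is not prognostic, but up to about 6 without them. Option 2 also needs ethics and regulatory submission under Protocol 10.2.3.
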